## Data Collection Procedures

### Baseline Phone Visit

At the baseline data phone visit, study staff conducted interviews to complete the baseline questionnaires: the modified ISAAC Core Questionnaire (a four-page questionnaire about asthma and associated diseases), the ISAAC Environmental Questionnaire (a one-page excerpt of a questionnaire regarding environmental exposures at home) and the baseline cooking survey (a two-page Questionnaire about cooking behaviors in the household and some demographic information about the parent). Portions of the ISAAC Core questionnaire assess general medical history (whether a child has ever had symptoms consistent with asthma, allergies or eczema), these questions were asked of all children. The questions specific to an asthma diagnosis were only asked of the children with asthma.

### Visit #2

The parent and child completed the same pre-visit surveys, and at the visit the child performed the same lung function testing. They were given the educational intervention, consisting of watching the video and receiving a reminder card and magnet. The equipment in place at the home was checked (anemometer, thermocouples, eLichens). The Ogawa passive sampler was exchanged for a new one. If air flow in the range hood (or OTR) was less than 100 cfm or noise levels are intolerable (>60 dBA) for settings >100 cfm, the range hood was

replaced with a functioning range hood model during or prior to this visit, if feasible within the study timeframe and budget.

#### Visit #3

The parent and child completed the same pre-visit surveys, and at the visit the child performed the same lung function testing. The equipment in place at the home was collected (anemometer, thermocouples, eLichens, Ogawa).

#### Power Considerations

This is a pilot study, and with COVID-related delays and adjustments, we were not able to complete the study with enough households to be fully powered for either exposure analyses or respiratory health outcomes (especially as the study was modified to include all children, rather than only those with asthma). However, the initial power calculation is retained here, to document the intended recruitment and that we acknowledge that we are underpowered.

In THE AQUA study the adjusted mean difference in  $PM_{2.5}$  between homes that used the range hood (ever) and those that never did was  $5 \mu g/m^3$  (standard deviation 8.24). (19) Using Cohen's equations for t-tests (assuming  $\alpha = 0.05$  and  $\beta=0.2$ ), if we expect to see at least a  $7 \mu g/m^3$  difference with an intentional cooking ventilation intervention, we would expect to be able to detect that difference with 23 households. Belanger and colleagues(21) showed an average  $NO_2$  level in homes of kids with asthma in Massachusetts was roughly 10 ppb, and low-income homes that use gas stoves a lot ( $>1h/day$ ) have  $NO_2$  levels 2-5 times those that do not.(6) In a study out of Lawrence Berkeley Lab, in homes expected to have high  $NO_2$ ,  $NO_2$  levels were roughly 10 ppb higher in homes with gas cooking. Thus we estimate that a ventilation intervention in homes with gas cooking could optimistically decrease  $NO_2$  7 ppb. To detect a difference of this size requires 28 households.

An intentional use of kitchen ventilation may decrease the  $PM_{2.5}$  levels by  $10 \mu g/m^3$  or more, which could decrease FeNO in asthmatic children by 7 ppb based on work by Mar et al, showing a decrease in FeNO based on prior day  $PM_{2.5}$  averages.(23) The minimum detectable change in FeNO for a group size of 30 is 3.3 ppb. Stanojevic et al (24) report that the coefficient of variation for FEV1 in children with asthma is around this age is roughly 10%, suggesting a standard deviation of roughly 10. For 30 children, the minimum detectable effect size will be 0.296, or a minimum detectable FEV1 difference of 2.9 percent of predicted.

#### Framework

Though our preference is to report estimates and confidence intervals, because we have pivoted to the use of Wilcoxon-Signed Rank tests (which do not generate an estimate), we will report  $p$  values for statistical tests.

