V4- As we are completing analyses, we realized that the changes made in versions 2-3 necessitate a couple additional edits that we had not foreseen. (1) We have edited the statistical framework section to note that we will use a p cutoff of <0.05 to determine statistical significance; (2) multiple imputation will not be attempted due to the small sample size; (3) we added a note that initial processing of the continuously monitored data was done in python; and (4) sensitivity analyses that relied on the addition of a potential confounding variable are not feasible so we will instead look for graphical patterns.

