## Statistical Principles

### Confidence Intervals and p-values

*P*-values less than 0.05 will be used as the threshold for significance.

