### Analysis Populations

All households for which we collected data for 3 or more cooking events both prior to and following the intervention will be included in exposure analyses. Children who successfully completed lung function testing both before and after intervention will be included in respiratory health outcomes. For households with data on more than one child, the child who has the most complete data (most spirometry and FeNO results that meet grading criteria for acceptable tests) will be used in the analyses.

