#### Identification and analysis of self-reported cooking data

The survey responses about cooking will be pulled from the electronic data collection system for the 1 or more weeks prior to the intervention and 1 or more weeks after the intervention. (Pull from REDCap download directly to R)

- How often was the gas stove or oven used in your home over the last week: Breakfast, lunch, dinner, other times (never, 1-2 days, 3-4 days, 5+ days)
- If food was being cooked, how often was it: Fried, deep fried, grilled, steamed/boiled, toasted, electric pot cooker, baked, microwaved
- Think about the burner you used the most this week. Is it one of the burners in the front or back? (front/back/my stove doesn't have front and back burners)
- In the last week, how often was the stove hood fan used during cooking? (never, rarely, occasionally, frequently)

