  - Peaks that occur within 10 min of each other (also an imprecise threshold based on experience of the research team), with intervening concentrations not dropping to <50% of the level of the first peak, shall be considered as being part of the same event.
  - Determine an event baseline based on the fitted baseline / background.
  - Events for which algorithmic classification provides nonsensical or undetermined results will be flagged and evaluated visually by at least two researchers.

For each pollutant event (PM2.5, NO2, CO2), we will calculate the following statistics:

- Event statistics:
  - start time and end time of *increasing* concentrations (i.e., not including the decay)
  - duration of emissions event
  - time of return to baseline (based on fitted baseline)
  - end of decay interval.
- Pollutant statistics:
  - prominence (highest ten-minute average above baseline) of each pollutant
  - integrated concentration of each pollutant above baseline (ug/m^3-min)

Notes:

- There should be few or no NO2 events that are not linked to cooking.
- There are unlikely to be any sharp CO2 events not linked to cooking; but there will be CO2 events linked to occupancy.
- There could be many PM2.5 events not linked to cooking.

All events identified by algorithms (Burners, cooking, range hood, PM2.5, NO2, CO2 increases) will be visually reviewed and any that are not deemed to be clearly correct will be reviewed and discussed with a second researcher.

Calculate Summary Statistics for each home during each of the pre- and post-intervention periods:

- Primary summary statistics of cooking and range hood events
  - Number of discrete events of individual burner use (confirmed and confirmed + possible) for cooktops, ovens, and any burner.
  - Number of cooking events.
  - Number and fraction of cooking events with substantial particle emissions.
  - Total burner minutes.
  - Mean (SD) number of burners used and burner minutes per cooking event (as an indicator of similarity).
  - Delay from start of cooking to start of range hood use.
  - Fraction of total burner minutes that reflects usage of the front burners and fraction that reflects usage of the back burners.
  - Fraction of cooking events with any range hood use.
  - Fraction of cooking events with range hood used for >80% of cooking burner use.

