## Outcome Definitions

At the baseline phone visit, health information was collected using the validated Isaac Questionnaires developed for use with 6-7 year-olds.(25) The core Isaac questionnaire contains 8 questions on asthma history, 6 on allergy history and 7 regarding history of eczema.

Children with asthma (with their parent) completed an asthma control test prior to or during each study visit. Study staff were trained on administering spirometry and FeNO tests for all participants, which occurred at follow up visits initially and later in the study was added to the initial visit to give children time to learn the techniques. These measures of respiratory status will be continuous variables.

The study used an EasyOne Spirometer, which was brought to the homes. Under the supervision of study staff, each child performed spirometry to complete three acceptable efforts (maximum eight attempts), in accordance with standard ATS/ERS performance criteria.(27) Each effort will be graded by a trained physician, in accordance with the 2019 ATS/ERS guidelines. If there are two or more efforts with acceptable quality and reproducible FEV1 and FVC (each  $\leq 0.15L$ ), the best FEV1 and best FVC will be used. If two or more efforts had usable quality and reproducible FEV1, but unacceptable FVC, only the best FEV1 will be used and FVC will be set to missing.

Each child also had a FeNO measured in accordance with ATS/ERS criteria,(28) by blowing a steady sustained exhalation into a NIOX Vero device to complete 2 measurements with exhalation duration greater than 10 seconds, and within 10% of each other (maximum eight attempts). If there are two measurements within 10%, this testing session will be graded as acceptable and the larger value will be used. If there are one or multiple FeNO measurements of adequate duration (but none within 10%), this testing session will be graded as usable and these values will be averaged to create the FeNO value for analysis.

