## Analysis Methods

**Determine if a cooking ventilation intervention (not receiving anything, receiving education only, or receiving education and range hood replacement) is associated with changes in (1) ventilation, (2) front vs back burner use, (3) household particulate matter, (4) NO2 and (5) CO2 levels.** We will use a

Wilcoxon Signed Rank test to compare the pre-intervention data to the post-intervention data to assess the relationship between intervention status and the following variables.

1. Range hood use, characterized 4 ways:

- fraction of cooking events with any range hood use (this will be primarily estimated using the vane anemometer data, but can also be assessed with self-reported (weekly) range hood use frequency)
- fraction of cooking events with  $\geq 80\%$  range hood use
- fraction of cooking-linked pollutant events with substantial range hood use
- mean delay between start of cooking and start of range hood use

2. Front versus back burner use, characterized 2 ways

- fraction of total burner minutes that reflects usage of the front burners and fraction that reflects usage of the back burners.
- self-reported most common burner use

[figure not shown]
3. PM2.5 levels, characterized four ways:

- mean prominence (increase above baseline) of PM2.5 during cooking-linked pollutant events
- mean ug/m^3-min PM2.5 aggregated during cooking-linked pollutant events
- total magnitude of emissions (aggregated PM2.5 during cooking-linked pollutant events divided by burner minutes)
- time-integrated PM2.5 (if discernible from the data)

4. Nitrogen dioxide levels, characterized four ways:

- mean prominence (increase above baseline) of NO2 during cooking-linked pollutant events
- mean ppb-min NO2 aggregated during cooking-linked pollutant events
- total magnitude of emissions (aggregated NO2 during cooking-linked pollutant events divided by burner minutes)
- time-integrated NO2

5. Mean prominence of carbon dioxide during cooking-linked pollutant events

In general, the covariates that will vary over time (eg. total burner use minutes) are not related to the intervention status and thus do not need to be controlled in order to prevent bias.

Given the small final sample size, these will not be adjusted in the analysis (but original DAG maintained for completeness).

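### The SAP drops estimates and confidence intervals for a reason that does not hold, and tests ACT at p<0.05 with at most four pairs, where an exact test cannot reach that threshold

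*SAP*

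**What the plan says.** The Framework section of the SAP states a preference for estimates and confidence intervals. It then turns to p-values "because we have pivoted to the use of Wilcoxon-Signed Rank tests (which do not generate an estimate". The V4 entry in the revision log adds the cutoff: "we will use a p cutoff of <0.05 to determine statistical significance". The section Confidence Intervals and p-values repeats it for p: "values less than 0.05 will be used as the threshold for significance". Neither place states whether tests are one-sided or two-sided.

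Analysis Methods applies the signed-rank test, before against after, to every exposure outcome and to FeNO, FEV1, FEV1/FVC and the ACT score, with no exception for ACT. Outcome Definitions says who provides ACT: "Children with asthma (with their parent) completed an asthma control test prior to or during each study visit". Sensitivity Analyses reports that four completing households had a child with asthma. Analysis Populations keeps one child per household and adds a further condition: "Children who successfully completed lung function testing both before and after intervention will be included in respiratory health outcomes".

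The descriptive plan is headed "Calculate Summary Statistics for each home during each of the pre- and post-intervention periods". It lists means, SDs and fractions by home and period.

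**The concern.** Two defects follow from the move to signed-rank tests.

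First, the only reason given for abandoning the preferred form of reporting fails. The stated objective is a pilot that explores whether the intervention could improve exposures and health. With 14 households and acknowledged low power, non-significant results are likely. A p-value cannot then separate a change that is small from a change that was measured too imprecisely to judge. An interval can, and the SAP gives it up unnecessarily.

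Second, ACT faces a significance threshold that an exact test cannot meet at the available number of pairs. A report that ACT did not change significantly would read as evidence about the children, although the verdict was settled by the sample size.

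**Working it through.** **Inputs**

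- Households completing: 2 + 5 + 7 = 14 (SAP, Study Design); Analysis Methods also gives 14 participants.
- ACT pairs: at most 4 (Sensitivity Analyses, Outcome Definitions, one child per household in Analysis Populations). Missing Data specifies complete cases, so a missing score lowers this number. A zero change also lowers the number of pairs that the test uses.
- Threshold: 0.05. Sidedness is not stated, so both cases are shown.

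The documents give no smallest attainable p-value and no precision for a paired change, so there is no planned figure to reproduce.

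**Step 1: is an estimate available?** For n paired differences, form all n(n+1)/2 Walsh averages (the mean of each pair of differences, including each difference with itself). Their median is the Hodges-Lehmann shift. Let k be the largest value with P(W ≤ k) ≤ 0.025 under the exact null distribution of the signed-rank statistic W. Dropping k Walsh averages at each end gives the confidence interval, with exact coverage 1 − 2P(W ≤ k).

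For n = 14 there are 14 × 15/2 = 105 Walsh averages and k = 21. The interval therefore runs from the 22nd smallest to the 22nd largest.

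| Pairs | k | Exact coverage | Mean half-width (SDs of the paired differences) |
|---|---|---|---|
| 14 | 21 | 95.06% | 0.58 |
| 12 | 13 | 95.75% | 0.66 |
| 10 | 8 | 95.12% | 0.71 |
| 8 | 3 | 96.09% | 0.88 |
| 6 | 0 | 96.88% | 1.27 |

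The half-widths are simulated and assume normal differences. At n = 14 they become 0.45 for t-distributed differences with 3 df and 0.39 for lognormal differences with log-SD 1. The documents give no SD for paired differences, so no value in pollutant units can be stated. Fourteen is the most favourable number of pairs, because Analysis Populations can reduce it.

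**Step 2: do the planned summaries fill the gap?** The summary statistics describe each home in each period, and pollution events are aggregated before and after. They feed the comparison. No section plans a paired change across homes with an interval.

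**Step 3: the floor for ACT.** The smallest exact two-sided p with n non-zero differences, all in one direction, is 2/2^n.

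- n = 3: 2/8 = 0.25
- n = 4: 2/16 = 0.125 (one-sided 1/16 = 0.0625)
- n = 5: 2/32 = 0.0625
- n = 6: 2/64 = 0.031, the first value below 0.05

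Ties in the size of change leave the exact permutation floor at n = 4 unchanged at 0.125.

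**Step 4: can an approximation fall below 0.05?** With ties, R's default is a continuity-corrected normal approximation. For four positive changes, W = 10 with null mean 5 and variance equal to the sum of squared ranks divided by 4, so z = (5 − 0.5)/√variance.

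| Pattern | Variance | Two-sided p |
|---|---|---|
| One tied pair | 7.375 | 0.098 |
| Two tied pairs | 7.25 | 0.095 |
| Three tied | 7.00 | 0.089 |
| All tied | 6.25 | 0.072 |

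Values below 0.05 appear only in two ways. Without the continuity correction and with all four changes identical, z = 5/2.5 = 2 and p = 0.0455. One-sided with ties and the correction, p lies between 0.036 and 0.049. Both are artefacts of the approximation, since the exact one-sided value is 0.0625.

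**Step 5: an interval for ACT.** At n = 4 the widest exact interval covers 1 − 2/16 = 87.5%. An exact 95% interval does not exist for ACT either.

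**The case against.** The wording in Framework is literally true of the bare test, which yields a statistic and a p-value; in R the estimate and interval must be requested. That stands, but it does not justify dropping them.

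Readers would not see p-values alone, because before and after means, SDs and fractions are planned. This also stands in part: the rough size of a difference would be visible. What is missing is a paired summary across homes and any statement of its uncertainty.

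The SAP is open about its limits. Power Considerations says the study is underpowered, names respiratory outcomes and notes that opening enrolment to all children made this worse. Sensitivity Analyses says the asthma subgroup may be too small to show anything, and plans only to observe its statistics. That remark is the nearest the SAP comes to disclosure, but it concerns the subgroup analysis, not the main ACT comparison. Low power means significance is unlikely; here an exact test makes it impossible.

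The half-widths depend on an assumed distribution. They are illustrative, and the defect does not rest on them.

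Finally, V4 was written while analyses were being completed, so any change comes late. That is a reason to log the change openly, and the change affects reporting only.

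**Conclusion.** The concern holds on both parts and should be fixed. The SAP can have the estimates and intervals it says it prefers, from the test it has already chosen. An exact interval of at least 95% exists for any outcome with six or more untied, non-zero pairs. At 14 pairs its mean half-width is about 0.58 SD of the paired differences under normality. Reading the shift as a typical change also assumes that the paired differences are symmetric.

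For ACT, four pairs is an upper bound. The exact floor is 0.125 two-sided and 0.0625 one-sided, and R's two-sided default with ties goes no lower than 0.072. The significance verdict would carry no information, and the SAP does not say so. In an unadjusted pilot this is a defect of reporting and does not invalidate the study.

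**What to change.** - **Framework:** delete the parenthetical statement that the test gives no estimate. For each continuous or fraction outcome, report the number of pairs and the Hodges-Lehmann paired shift with its 95% interval, followed by the p-value. The interval is exact where there are no ties or zeros; otherwise use a method for ties and zeros that the SAP names.
- **Confidence Intervals and p-values:** state sidedness and the symmetry assumption.
- **Analysis Methods, exposure outcomes:** the category "self-reported most common burner use" and the ordinal item "how often was the stove hood fan used during cooking? (never, rarely, occasionally, frequently" do not suit a shift estimate. Give counts of homes that changed in each direction. State how hood delay is handled in a home with no hood use in one period, where it may be undefined.
- **Analysis Methods, ACT:** replace the test with each child's values before and after and the median change. State that p<0.05 is unattainable with an exact test at this number of pairs.
- **Sensitivity Analyses:** confirm that no significance reading will be attached to the four-household asthma subgroup. The present text already leans this way.

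The cost is a short edit to these sections, one argument in the R call and a named method for ties and zeros, entered in the revision log as a late change. Data, population and design stay as they are.

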#### Interim Analysis and stopping guidance

The only interim analyses to be performed include summary statistics about basic cohort demographics, and discussion of the free-text comments from participants in their end of study survey. All other analyses have been held until data collection is complete.

#### Timing of Analysis and Outcome Assessments

While field data collection was initially planned for summer 2020, it was delayed until summer 2021, due to the onset of the COVID-19 pandemic. In the summer of 2021, a surge in cases related to the delta variant of SARS-CoV-2 made recruitment difficult. We made protocol changes as described in the study design section. All data collection has been completed prior to the finalization of the statistical analysis plan, though no analyses have been done (other than a few descriptive statistics for this SAP).

## Statistical Principles

### Confidence Intervals and p-values

*P*-values less than 0.05 will be used as the threshold for significance.

### Adherence and Protocol Deviations.

Not applicable

### Analysis Populations

All households for which we collected data for 3 or more cooking events both prior to and following the intervention will be included in exposure analyses. Children who successfully completed lung function testing both before and after intervention will be included in respiratory health outcomes. For households with data on more than one child, the child who has the most complete data (most spirometry and FeNO results that meet grading criteria for acceptable tests) will be used in the analyses.

## Study Population

### Cohort description

We recruited children ages 6-12, living in Richmond/ San Pablo/ El Cerrito/ Albany/ Berkeley/ Oakland/ Alameda. They were eligible for this study if the parent reported that they had both a gas stove and a venting range hood, i.e. one that extracted air from the kitchen to outdoors. They were excluded from the study if they lived with a smoker who smoked indoors, if they knew they would not have stable housing for the period of the study or if they were not fluent in English.

Recruitment occurred through East bay pediatric clinics where children are seen, using contacts previously established by the investigators. These clinics include Contra Costa Health System (CCHS) Clinics, UCSF Benioff Children's Physicians-Hilltop Pediatrics Clinic, Lifelong-Jenkins clinic, Kiwi pediatrics and UCSF Benioff Children's Hospital Oakland (BCHO) Outpatient clinics. We posted recruitment fliers in the clinics and had study information cards that physicians and staff could give to children with asthma. At a few clinics postcard mailings were sent to potentially eligible patients.

Due to the paucity of in-person visits happening at the Contra Costa County Health Clinics and Hilltop, recruitment at those sites was supplemented in the spring of 2021 with a postcard mailing to all patients aged 6-12 with a diagnosis of asthma. Recruitment fliers and cards were also posted in community spaces where kids and families may spend time (e.g. local library), and at other clinics where no staff are participating in any recruitment activities (not handing out cards or otherwise). Digital flyers are also distributed to school districts and to other community organizations that regularly distribute materials to families, for inclusion in their outreach (newsletters, digital bulletin boards). We have also been advertising the study on our webpage and through social media.

